Attachment 2: HIV-risk Assessment

The following are intended as guidelines for the investigator to help identify potential vaccine trial participants at “low risk” for HIV infection in the US and Switzerland. Outside these countries, in addition to minimum requirements specified by the first two criteria defined below (“Have oral, vaginal or anal intercourse with an HIV-infected partner, or a partner who uses injection drugs” and “Give or receive money, drugs, gifts or services in exchange for oral, vaginal or anal sex”), low risk criteria as defined by local standards would be applicable.

**HVTN Low Risk Guidelines**
August 1, 2013**HIV VACCINE
TRIALS NETWORK**

The following are intended as guidelines for the investigator to help identify potential vaccine trial participants at “low risk” for HIV infection in the US and Switzerland. These guidelines are based on behaviors within the last 6-12 months prior to enrollment; however, it may be appropriate to consider a person’s behavior over a longer period of time than specified to assess the person’s likelihood of maintaining low risk behavior. *Some volunteers may not be appropriate for enrollment even if they meet these guidelines.* These guidelines should be supplemented and interpreted with local epidemiologic information about HIV prevalence in your area and community networks. The investigator may review the risk level of any volunteer with the site PI and/or the Protocol Safety Review Team.

A volunteer may be appropriate for inclusion if he/she meets these guidelines:

1. SEXUAL BEHAVIORS

In the **last 12 months** did not:

- Have oral, vaginal, or anal intercourse with an HIV-infected partner, or a partner who uses injection drugs
- Give or receive money, drugs, gifts, or services in exchange for oral, vaginal, or anal sex

AND

In the **last 6 months** has abstained from penile/anal or penile/vaginal intercourse, OR

In the **last 6 months**:

- Had 4 or fewer partners of the opposite birth sex for vaginal and/or anal intercourse, OR

Is an MSM (person born male with partner(s) born male) who, in the **last 12 months**:

- Had 2 or fewer MSM partners for anal intercourse and had no unprotected anal sex with MSM, OR
- Had unprotected anal intercourse with only 1 MSM partner, within a monogamous relationship lasting at least 12 months (during which neither partner had any other partners). If the monogamous relationship ended, the volunteer may then have had protected anal intercourse with 1 other MSM partner (total 2 or fewer partners in the last 12 months).

Is a transgender person, regardless of the point on the transition spectrum, having sex with men (born male) and/or other transgender persons, who **in the last 12 months**:

- Had 2 or fewer partners for anal or vaginal intercourse, and had no unprotected anal or vaginal sex, OR
- Had unprotected anal or vaginal intercourse sex with 1 partner only within a monogamous relationship lasting at least 12 months (during which neither partner had any other partners). If the monogamous relationship ended, may then have had protected anal or vaginal sex with 1 other partner (total 2 or fewer partners in the last 12 months).

AND

Uses or intends to use condoms in situations which may include penile/anal or penile/vaginal intercourse with new partners of unknown HIV status, occasional partners, partners outside a primary relationship, and/or partners known to have other partners.

2. NON-SEXUAL BEHAVIORS

In the **last 12 months** did not:

- Inject drugs or other substances without a prescription
- Use cocaine, methamphetamine, or excessive alcohol, which in the investigator's judgment, rendered the participant at greater than low risk for acquiring HIV infection

The investigator's judgment should consider local epidemiologic information about HIV prevalence in the area and community networks.

A volunteer is NOT appropriate for inclusion if he/she:

Acquired an STI (ie, new infection) in the last 12 months:

- Syphilis
- Gonorrhea
- Non-gonococcal urethritis
- HSV-2
- Chlamydia
- Pelvic inflammatory disease (PID)
- Trichomonas
- Mucopurulent cervicitis
- Epididymitis
- Proctitis
- Lymphogranuloma venereum
- Chancroid
- Hepatitis B

Attachment 3: Test of Understandingⁱ

Please read each question and answer whether the statement is **True** or **False**.

True 	False 	1. The vaccines you will receive in this study protect against HIV.
<hr/>		
True 	False 	2. You will need to come to the clinic for 4 scheduled visits over the next 1.5 years.
<hr/>		
True 	False 	3. The vaccines in this study can give you HIV.
<hr/>		
True 	False 	4. One purpose of this study is to determine if these vaccines are safe to administer to humans.
<hr/>		
True 	False 	5. Participants in this study will need to avoid engaging in activities that may expose them to HIV infection.
<hr/>		
True 	False 	6. You may take other experimental (test) products while you are taking part in this study.
<hr/>		
True 	False 	7. You may withdraw from the study at any time if you choose or your participation may be stopped if the study team decides it is in your best interest.
<hr/>		
True 	False 	8. Women participating in this study are permitted to become pregnant starting 3 months after the last vaccination.
<hr/>		
True 	False 	9. A participant in this study may experience side effects after vaccination.
<hr/>		
True 	False 	10. Some participants in this study may develop a positive HIV-test result, despite the fact that they are not HIV infected.

ⁱ Adaptations to the TOU are allowed for local purposes, after IRB and sponsor approval.

Attachment 4: Social Impact Questionnaire**Vaccine Research Center (VRC) Social Impact Case Report Form^j**

	Social Impact Question	Yes or No	If Yes, did you consider this to be harmful to you?
1. Personal Relationships	Did you have problems with family, friends, significant others or sex partners because of participation in this clinical trial?	 Yes  No	 Yes  No
	Comment:  resolved;  continuing		 mild;  moderate;  major
2. Travel or Immigration	Did you have problems getting legal permission to travel to or from another country, such as being denied a visa, or having problems with immigration/naturalization because of participation in this clinical trial?	 Yes  No	 Yes  No
	Comment:  resolved;  continuing		 mild;  moderate;  major
3. Employment	Have you been turned down for a new job, lost a job, or had other problems at work because of participation in this clinical trial?	 Yes  No	 Yes  No
	Comment:  resolved;  continuing		 mild;  moderate;  major
4. Education	Have you been turned down by an educational program, told to leave an educational program, or had other problems at school because of participation in this clinical trial?	 Yes  No	 Yes  No
	Comment:  resolved;  continuing		 mild;  moderate;  major
5. Medical or Dental	Have you been refused medical or dental care or treated negatively by a health care provider because of participation in this clinical trial?	 Yes  No	 Yes  No
	Comment:  resolved;  continuing		 mild;  moderate;  major
6. Health Insurance	Have you lost health insurance, had a problem getting new health insurance, or had other problems related to health insurance because of participation in this clinical trial?	 Yes  No	 Yes  No
	Comment:  resolved;  continuing		 mild;  moderate;  major
7. Life Insurance	Have you lost life insurance, had a problem getting new life insurance, or had other problems related to life insurance because of participation in this clinical trial?	 Yes  No	 Yes  No
	Comment:  resolved;  continuing		 mild;  moderate;  major
8. Housing	Have you had trouble getting or keeping housing, or had other problems related to housing because of participation in this clinical trial?	 Yes  No	 Yes  No
	Comment:  resolved;  continuing		 mild;  moderate;  major
9. Military/Other Government Agency	Have you had a problem with the military or any other government agency because of participation in this clinical trial?	 Yes  No	 Yes  No
	Comment:  resolved;  continuing		 mild;  moderate;  major
10. Other	Have you had any other problem not covered by the other questions because of anything related to participation in this clinical trial?	 Yes  No	 Yes  No
	Comment:  resolved;  continuing		 mild;  moderate;  major

^j Adaptations to the social impact questionnaire are allowed for local purposes, after IRB and sponsor approval.

INVESTIGATOR AGREEMENT

I have read this protocol and agree that it contains all necessary details for carrying out this study. I will conduct the study as outlined herein and will complete the study within the time designated.

## AMENDMENT HISTORY

V1.0 19 March 2019	First version
V2.0 2 May 2022	Updated version to include long term extension data up to week 264

## ABBREVIATIONS

ADCP	antibody dependent cellular phagocytosis
AE	adverse event
BAMA	binding antibody multiplex assay
BIDMC	Beth Israel Deaconess Medical Center
BMI	body mass index
CI	confidence interval
CRF	case report form
CTP	clinical trial protocol
DAIDS	Division of AIDS
DP	drug product
DPS	data presentation specification
ELISA	enzyme-linked immunosorbent assay
ELISPOT	Enzyme-Linked ImmunoSpot
ENV	Envelope
FHCRC	Fred Hutchinson Cancer Research Center
GM	geometric mean
GMR	geometric mean ratio
HIV	human immunodeficiency virus
ICS	intracellular cytokine staining
IG	immunogenicity
LLOQ	lower limit of quantification
LOD	limit of detection
LTE	long term extension
PrEP	Pre-Exposure Prophylaxis
SAE	serious adverse event
SDTM	study data tabulation model
ULN	upper limit of normal
VRC	Vaccine Research Center
RBC	red blood cell
WBC	white blood cell

## DEFINITION OF TERMS

Randomization	5:1:10:2 ratio			
Study vaccine	
 
- Ad26.Mos4.HIV (Ad26.Mos.1.Env + Ad26.Mos.2.Env +Ad26.Mos1.Gag-Pol + Ad26.Mos2.Gag-Pol): Total dose is <math>5 \times 10^{10}</math> viral particles (vp) per 0.5 mL injection
 
- Ad26.Mos.HIV (Ad26.Mos.1.Env + Ad26.Mos1.Gag-Pol + Ad26.Mos2.Gag-Pol): Total dose is <math>5 \times 10^{10}</math> viral particles (vp) per 0.5 mL injection
 
- gp140 DP: gp140 DP with 250 mcg total protein, mixed with aluminum phosphate adjuvant (0.425 mg aluminum) at the pharmacy, per 0.5 mL injection
 
- Placebo: 0.9% saline, 0.5 mL injection
 
			
Vaccination compliance	Each vaccine administered (if applicable) according to planned schedule			
Vaccine regimen	Group	Planned N	Day 1, Week 12	Week 24, Week 48
	1A	55	Ad26.Mos.HIV	Ad26.Mos.HIV + gp140
	1B	11	Placebo	Placebo + Placebo
	2A	110	Ad26.Mos4.HIV	Ad26.Mos4.HIV + gp140
	2B	22	Placebo	Placebo + Placebo

## 1. INTRODUCTION

This statistical analysis plan (SAP) was initially written to describe the analyses of the main part of the study (up to Week 72). This updated version covers also the reporting of data collected till the end of the long-term extension (LTE) which lasted up to Week 264 (final analysis at end of study) for the group 2A receiving the full vaccination regimen ‘Ad26.Mos4.HIV/Ad26.Mos4.HIV + gp140’. At the time this SAP was written the Week 72 statistical analysis was already performed and will not be rerun. The below described analyses will be performed on fully unblinded data.

### 1.1. Trial Objectives

See CTP, Section 2.1.

### 1.2. Trial Design

See CTP, Section 3.1.

### 1.3. Statistical Hypotheses for Trial Objectives

No formal statistical hypothesis will be tested.

### 1.4. Sample Size Justification

See CTP, Section 11.2.

### 1.5. Randomization and Blinding

See CTP, Section 5.

## 2. GENERAL ANALYSIS DEFINITIONS

A baseline (or reference) value will be defined as the value of the last available assessment performed prior to the first dose (active vaccine or placebo).

### 2.1. Analysis Windows

The phases and periods in the study will be constructed as follows:

**Table 3: Phase and Period Definitions**

Phase	Phase number	Period	Period number	Interval	
				From	To
Screening	1			00:00 of the date of signing the informed consent form a	One minute prior to Dose 1 on Day 1
Regimen	2	Post-Dose 1	1	Date and time of Dose 1 (Day 1)	Minimum of: a) Maximum (28 days after first vaccination at 23:59, scheduled visit 4 weeks after first vaccination at 23:59) b) 23:59 at the date of last contact (for early discontinuation)

**Table 3: Phase and Period Definitions**

Phase	Phase number	Period	Period number	Interval	
				From	To
Follow-Up 1	3			1 minute after end of Post-Dose 1 period	Minimum of: a) One minute prior to date and time of the next vaccination b) 23:59 at the date of last contact (for early discontinuation)
Regimen	2	Post-Dose 2	2	Date and time of Dose 2 (Day 85)	Minimum of: a) Maximum (28 days after second vaccination at 23:59, scheduled visit 4 weeks after second vaccination at 23:59) b) 23:59 at the date of last contact (for early discontinuation) c) One minute prior to post-dose 3
Follow-Up 2	4			1 minute after end of Post-Dose 2 period	Minimum of: a) One minute prior to date and time of the next vaccination b) 23:59 at the date of last contact (for early discontinuation)
Regimen	2	Post-Dose 3	3	Minimum of Date and Time of the two Dose 3 Injections (Day 169)	Minimum of: a) Maximum (28 days after the third vaccination at 23:59, scheduled visit 4 weeks after third vaccination at 23:59) b) 23:59 at the date of last contact (for early discontinuation)
Follow-Up 3	5			1 minute after end of Post-Dose 3 period	Minimum of: a) One minute prior to date and time of the next vaccination b) 23:59 at the date of database cut-off c in case of interim c) 23:59 at the date of last contact (for early discontinuation)
Regimen	2	Post-Dose 4	4	Minimum of Date and Time of the two Dose 4 Injections (Day 337)	Minimum of: a) Maximum (28 days after fourth vaccination at 23:59, scheduled visit 4 weeks after fourth vaccination at 23:59) b) 23:59 at the date of database cut-off c in case of interim c) 23:59 at the date of last contact (for early discontinuation)
Follow-Up 4	6			1 minute after end of Post-Dose 4 period	Minimum of: a) Last available visit for completers b) 23:59 at the date of last contact (for early discontinuation) c

**NOTE:**

a The start time of screening phase is 00:00. In case an earlier date is available (e.g. for lab or vital signs then use the very first date in order to include all data)

b In case a dose is not administered, the observations end up in the previous Follow-Up phase

c This timepoint is intended to be at the end of the main study i.e. Week 72. LTE data will be reported separately

For the immunogenicity analyses no phases will be constructed.

The periods/phases will be used primarily for safety and concomitant medication allocation. The post-dose periods (and the regimen phase) are considered active periods/phase, the screening and follow-up phases are considered non-active phases. There will be no phase defined for the LTE part of the study.

For descriptive statistics over time, assessments (regardless of the investigated parameter) will be allocated to an analysis visit based on the visit number as captured in the database.

For subjects that received a first dose, but did not receive a 2nd dose while still continuing their planned visit schedule, the measurements after the planned but not administered 2nd dose will not be included in graphs and tables showing descriptive statistics over time. Those measurements will be shown in listings but it will be indicated that these are not used in the analysis. Moreover, the vaccinations done after a missed one will not be shifted to the previous one but will be considered as planned: in the example above if the 2nd is missed, the 3rd vaccination will still be reported as post-dose 3.

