9.1.2. Visit Windows

The maximum screening period is 4 weeks, with the exception of female subjects or female partners of male subjects starting hormonal contraception. In this case, the maximum screening period is 6 weeks.

For the study visits, following windows will be allowed as indicated:

- Visit 3: Day 8 ± 1 day
- Visit 4: Day 15 ± 5 days
- Visit 5: Day 29 ± 5 days
- Visit 6: Day 85 -1 week, +3 weeks (second vaccination)
- Visit 7*: Visit 6 + 14 days (Day 99) ± 5 days

- Visit 8*: Visit 6 + 28 days (Day 113) \pm 5 days
- Visit 9: Day 169 -1 week, +3 weeks (third vaccination)
- Visit 10*: Visit 9 + 14 days (Day 183) \pm 5 days
- Visit 11*: Visit 9 + 28 days (Day 197) \pm 5 days
- Visit 12: Day 253 \pm 5 days
- Visit 13: Day 337 -1 week, +3 weeks (fourth vaccination)
- Visit 14*: Visit 13 + 14 days (Day 351) \pm 5 days
- Visit 15*: Visit 13 + 28 days (Day 365) \pm 5 days
- Visit 16: Day 421 \pm 3 weeks
- Visit 17: Day 505 \pm 3 weeks
- Visit 18 to 22 inclusive and Visit 24-25 inclusive: Days 673, 841, 1009, 1177, 1345, 1681, 1849, \pm 4 weeks
- Visit 23: 1513 -4 weeks/+2 months

*If a subject is not vaccinated on the given day of vaccination, the timings of the visits 2 and 4 weeks post-vaccination (see [Time and Events Schedule](#)) will be determined relative to the actual day of vaccination.

If a subject cannot be vaccinated within the allowed window, then that vaccination should not be administered. However, if the window is missed due to a study pause (see [Section 11.9](#)), vaccination will be assessed on a case-by-case basis upon discussion between investigator and sponsor. If a subject misses more than 1 study vaccination, he/she will be withdrawn from further study vaccination.

For the LTE phase (from Week 72 onwards): If a visit can't be scheduled within the allowed window, it will be assessed on a case-by-case basis upon discussion between investigator and sponsor whether this visit can still be performed.

In the event of emergencies (possibly affecting a site, a region, a country or world-wide), it may not be possible to conduct all assessments at the defined time (or within the designated window). See [Section 9.1.1](#) and [Appendix 18, COVID-19 APPENDIX: GUIDANCE ON STUDY CONDUCT DURING THE COVID-19 PANDEMIC](#) for details.

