9.5. Sample Collection and Handling

The actual dates and times of sample collection must be recorded in the CRF or laboratory requisition form.

See the [Time and Events Schedule](#) for the timing and frequency of all sample collections.

Instructions for the collection, handling, storage, and shipment of samples are found in the Laboratory Manual that will be provided. Collection, handling, storage, and shipment of samples must be under the specified, and where applicable, controlled temperature conditions as indicated in the Laboratory Manual.

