18. COVID-19 APPENDIX: GUIDANCE ON STUDY CONDUCT DURING THE COVID-19 PANDEMIC

It is recognized that the Coronavirus Disease 2019 (COVID-19) pandemic may have an impact on the conduct of this clinical study due to, for example, self-isolation/quarantine by subjects and study-site personnel; travel restrictions/limited access to public places, including hospitals; study site personnel being reassigned to critical tasks.

In alignment with recent health authority guidance, the sponsor is providing options for study related subject management in the event of disruption to the conduct of the study. This guidance does not supersede any local or government requirements or the clinical judgement of the investigator to protect the health and well-being of subjects and site staff and to maintain oversight of delegated trial activities.

Scheduled visits that cannot be conducted in person at the study site will be performed to the extent possible as a remote visit, a home visit, or delayed until such time that on-site visits can be resumed.^g At each contact, subjects will be interviewed to collect safety data. Key endpoint assessments should be performed if required and as feasible. Subjects will also be questioned regarding general health status to fulfill any physical examination requirement.

Every effort should be made to adhere to protocol-specified assessments. Modifications to protocol-required assessments may be permitted via COVID-19 Appendix after consultation with the subject, investigator, and the sponsor. Missed assessments/visits will be captured in the clinical trial management system for protocol deviations. Discontinuations of study interventions and withdrawal from the study should be documented with the prefix “COVID-19-related” in the case report form (CRF). Any deviations to study procedures occurring due to the COVID-19 pandemic need to be properly captured in the clinical trial management system (or CRF), with the prefix “COVID-19-related” (including actual visit date) and will be summarized in the clinical study report.

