#### Humoral response

For all the humoral assays the immune response values will be  $\log_{10}$ -transformed before any further handling. The  $\log_{10}$ -transformed values will be used throughout the analysis. In the graphs, original values will be displayed on the  $\log_{10}$  scale.

For each assay and at each time point geometric mean of actual values, geometric mean increases and percentage of responders, all with corresponding 95% CIs will be provided in the tables. Also, mean fold change from highest post-baseline value to week 72 will be reported. The definition of responders is defined in section 6.4 for each assay. Graphical presentations will be provided displaying dots for the subject values and including the geometric mean and the percentage of responders. If available, baseline values will be summarized pooling all the groups and will be displayed on the left of each graph. Data from post-baseline timepoints will be plotted next to each other for each group, a symbol will identify the geometric mean (or the median) of each group and timepoint.

In the graphs the actual values will be shown and the LLOQ cut-off will be visualized, the values below LLOQ or below LOD will be visualized with the value imputed as described in section 6.3.

Graphs by subgroups listed in section 2.4 will be done for Elisa Clade C (C97ZA.012), ADCP Clade C (C97ZA.012).

Durability will be shown as a line plots displaying the GM/median for each vaccine regimen.

Magnitude-breadth (MB) plot for the ELISA assay will be provided at each timepoint to explore the magnitude and breadth of each individual serum sample assayed (antibody titers of 5 Clades). MB curves will show, for each possible titer threshold, the proportion of antibody titers greater than this threshold. The group-specific curve obtained as the average MB across all subjects in that group will be displayed. The AUC-MB is calculated as the average of the titers over the panel of antigens.

For BAMA the median will be reported instead of the geometric mean. Cumulative number of responses across the IgG/antigen classes will be tabulated.

Magnitude-breadth (MB) plots for the BAMA assay will be provided at week 28 to explore the magnitude (MFI of IgG3 and of IgG breath binding antibodies) and breadth of each individual serum sample assayed. MB curves will show, for each possible MFI threshold, the fraction of antigens with MFI greater than this threshold.

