### **Cellular response**

For ELISpot and for each peptide: n, median, quartile range, min, max of actual values, percentage of responders above a predefined threshold (see section 6.4) and corresponding 95% CI will be tabulated.

Graphical presentations will be provided displaying dots for the subject values and including the median and the percentage of responders. In the graphs the actual values will be shown and the LLOQ cut-off will be visualized, the values below LLOQ will be visualized with the value imputed as LLOQ/2.

In the graphs, original values will be displayed on the  $\log_{10}$  scale. Graphs by subgroups listed in section 2.4 will be done for ELISpot Env peptide pool PTE, Gag peptide pool PTE and Pol peptide pool PTE.

ICS

*T cells: CD4+, CD8+*

*Antigen: Combined pools and separated pools*

Cytokine counts: Marginal, Boolean AND (co-expression) counts, Boolean OR (and/or)

For CD4+ and CD8+ and for each antigen (combined and separated pools): n, median, quartile range, min, max, percentage of responders (see section 6.4) and corresponding 95% CI will be tabulated for each available cytokine background adjusted percentages listed below.

Cytokine (ISSCAT)	Description
CD154+	Marginal
GzB+	Marginal
ICOS+	Marginal
IFNg+	Marginal
IL2+	Marginal
IL17a+	Marginal
IL4+	Marginal
TNFa+	Marginal
IFNg+/IL2+	Boolean AND (co-expression)

Cytokine (ISSCAT)	Description
IFNg+/IL2+/TNFa+	Boolean AND (co-expression)
IFNg+/TNFa+	Boolean AND (co-expression)
IL2+/TNFa+	Boolean AND (co-expression)
IFNg+ or IL2+	Boolean OR (and/or)
IFNg+ or IL2+ or TNFa+	Boolean OR (and/or)

Graphical presentations will be provided displaying dots for the subject values and including the median and the percentage of responders. In the graphs the actual values will be shown and the LLOQ cut-off will be visualized, the values below LLOQ will be visualized with the value imputed as LLOQ/2.

In the graphs, original values will be displayed on the  $\log_{10}$  scale.

The technical details for the calculation of the cytokine background adjusted percentages to be displayed in the above described outputs will be outlined in the DPS.

Additional timepoints and tests within one of the above listed assays may be investigated for exploratory purposes. These data and data from timepoints belonging to the long-term extension part of the study will be analyzed using the approaches described above.

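### Long-term extension samples are placed by visit number with no analysis window, so the durability curve does not show the actual time since dose 4

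*SAP*

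**What the plan says.** SAP 2.1 places data on the time axis by label: "assessments (regardless of the investigated parameter) will be allocated to an analysis visit based on the visit number as captured in the database". It adds "For the immunogenicity analyses no phases will be constructed", and it defines no phase for the LTE, so no date-based allocation replaces the label. SAP 6.3 states that "data from timepoints belonging to the long-term extension part of the study will be analyzed using the approaches described above". The main display is described there as "Durability will be shown as a line plots displaying the GM/median for each vaccine regimen".

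The protocol's LTE timing is looser than one fixed week per visit. Section 9.1.2 gives Visits 18 to 22 and 24 to 25 a window of 4 weeks either side of the planned day. For the Week 216 visit it gives "Visit 23: 1513 -4 weeks/+2 months", which the LTE Time and Events footnote converts to -28/+60 days. Beyond the windows, "If a visit can't be scheduled within the allowed window, it will be assessed on a case-by-case basis upon discussion between investigator and sponsor" whether the visit can still take place. The COVID-19 appendix (Section 18) allows a visit that cannot be held on site to be done remotely, done at home, or "delayed until such time that on-site visits can be resumed". Neither provision states a maximum delay.

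The dates needed for an actual-time analysis are collected. Section 9.5 says "The actual dates and times of sample collection must be recorded in the CRF or laboratory requisition form", and Section 7 requires the date and time of each vaccination in the CRF.

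**The concern.** The LTE was added to show how long responses last after the fourth dose, so elapsed time is the horizontal axis of its main question. Under the SAP rule a sample is shown at the week its visit was planned for, whenever it was drawn. If responses are declining, a late sample lowers the value shown at its nominal week and makes the step to the next visit look flatter. An early sample does the reverse.

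No SAP rule catches this. The LTE analysis set (2.3.3) has no sample-timing criterion. The only sample-level timing exclusion in the per-protocol set (2.3.2) concerns when dose 4 was given, not when blood was drawn. SAP version 2.0 (2 May 2022) was issued to cover LTE data and postdates Amendment 4 (28 July 2020), which brought in both the case-by-case provision and the COVID-19 appendix, but it does not address them.

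**Working it through.** **Reproducing the schedule.** Planned day = 7 × week + 1. Weeks 96, 120, 144, 168, 192, 216, 240 and 264 give Days 673, 841, 1009, 1177, 1345, 1513, 1681 and 1849, all as in Section 9.1.2. The Visit 23 window is 4 × 7 = 28 days before and 2 × 30 = 60 days after, as the footnote states.

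**Visit 23 on the study-day clock.** The window runs from Day 1513 - 28 = 1485 to Day 1513 + 60 = 1573. Day 1573 is Week (1573 - 1)/7 = 224.6, but an in-window sample from that day is reported at Week 216. The Visit 24 window opens on Day 1681 - 28 = 1653. That leaves 1653 - 1573 = 80 days belonging to neither window, where the visit number alone decides placement.

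**Visit 23 on the dose 4 clock.** Dose 4 is planned for Day 337, -1/+3 weeks, so Day 330 to Day 358. Section 9.1.2 re-times only the visits 2 and 4 weeks after a vaccination to the actual dose; LTE visits stay on fixed study days. Days since dose 4 under the Week 216 label are then:

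- shortest: 1485 - 358 = 1127
- nominal: 1513 - 337 = 1176
- longest: 1573 - 330 = 1243

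The spread is 1243 - 1127 = 116 days with every protocol window respected. The SAP per-protocol set may change the limits. If its 2-week allowance extends the protocol window, as SAP 4.4 suggests, dose 4 may fall from Day 316 to Day 372 and the range becomes 1113 to 1257. If it means 2 weeks either side of Day 337, later-dosed subjects lose these samples and the lower end becomes 1485 - 351 = 1134.

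At every other LTE visit the compliant spread is 56 days (visit window) + 28 days (dose 4 window) = 84 days.

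**Effect on a value.** The documents give no decay rate, so half-lives of 6, 12 and 24 months (26, 52 and 104 weeks) are assumed, with log-linear decline. Relative value = 2^(-d/h), where d is the time difference and h the half-life.

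| Time difference | 6 months | 12 months | 24 months |
|---|---|---|---|
| 4 weeks late (edge of ordinary window) | 0.90 | 0.95 | 0.97 |
| 60 days late (edge of Visit 23 window) | 0.80 | 0.89 | 0.94 |
| 84 days (compliant extremes, other LTE visits) | 0.73 | 0.85 | 0.92 |
| 116 days (compliant extremes, Visit 23) | 0.64 | 0.80 | 0.90 |

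The first two rows compare one late sample with its on-time value. The last two compare the two most extreme compliant subjects under one label.

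**Effect on a group geometric mean.** If a share f of samples is late by d and the rest are on time, the ratio is 2^(-f·d/h). With f = 25% and d = 60 days this gives 0.94, 0.97 and 0.99. With f = 25% and d = 12 weeks it gives 0.92, 0.96 and 0.98. The value of f is an assumption.

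**The case against.** The strongest reply is that a prespecified summary by nominal visit is a transparent choice and that the stakes are small. LTE durability is an exploratory endpoint, described in one arm with no LTE control and no formal hypothesis. No primary or secondary result, type I error or power figure depends on it. That stands, and it limits the weight of the point.

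A reader might infer that the protocol removed all limits on late LTE visits. It did not. The windows remain, and a visit outside them needs a discussion between investigator and sponsor that may end in refusal. What is missing is a stated maximum for a visit that is allowed.

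A reader might also infer that the curve is known to be distorted, or accurate early and wrong during the pandemic. The documents show neither. They do not report any out-of-window sample or say which visits fell in the pandemic. Visits 18 to 22 and 24 to 25 share one window. Remote safety visits could produce missing samples instead of late ones. A delay of a full visit interval, 168 days, with the earlier label kept would give much larger errors, but nothing in the documents suggests it happened.

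Lateness would be partly visible. COVID-related deviations are recorded with the actual visit date and summarised in the study report (Section 18), and major deviations are listed (SAP 4.5). Protocol 11.2 would also exclude samples with major deviations expected to affect immunogenicity. These safeguards are incomplete: 11.2 does not name late samples, SAP 2.3.2 does not carry its general rule over, and none of them re-times a sample that stays in the analysis.

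**Conclusion.** The point holds as a limited improvement to an exploratory output. Following the SAP as written plots LTE samples at nominal weeks that can differ materially from time since dose 4, even when every protocol window is met: 1127 to 1243 days under the single label Week 216. For one sample 60 days late at Visit 23 the reading is about 80%, 89% or 94% of the on-time value, on assumed half-lives of 6, 12 and 24 months. Group values move less, in proportion to the share of late samples, which is unknown. With a declining response, late samples understate durability at their nominal week, and samples up to 4 weeks early err the other way, so the net direction cannot be stated from the documents.

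**What to change.** Keep the visit-number tables as the prespecified summary. For LTE immunogenicity outputs, add to SAP 2.1 and 6.3:

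1. Derive days since dose 4 from the recorded vaccination and sample dates.
2. Draw the individual and group durability curves on that axis. A simple group version places each visit's geometric mean at the mean observed days since dose 4; under log-linear decline with a common slope, that is the time to which the mean belongs.
3. List LTE samples taken outside the protocol window, with the size of the departure.
4. Add a sensitivity summary restricted to in-window samples.

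Item 4 does not replace item 2, because in-window samples can still lie 116 days apart at Visit 23. Reassigning each sample to the nearest planned week is not a good substitute. A limit of 84 days either side (half the 168-day spacing) would leave a sample 60 days late at Week 216, and planned weeks count from Day 1 whereas durability counts from dose 4.

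The cost is one derived variable and a few extra outputs for a descriptive endpoint in Group 2A. The Week 72 analysis, which the SAP says will not be rerun, is untouched. If few samples were late, the listing will show it.
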